10.2.4 SAFETY ANALYSES

The safety analyses will be performed on the SA population.

All treatment emergent adverse events (TEAEs), defined as events which were not present at baseline or worsened in severity following the start of treatment, will be reported according to NCI Criteria. The incidence of TEAEs will be summarized according to MedDRA coded primary system-organ class (SOC) and preferred term (PT). The summaries will be presented overall (severity grades 1-5) and for grade ≥ 3 events and by treatment discontinuation. These summaries will present the number and percentage of patients reporting an adverse event for each classification level as well as the number of events reported.

Serious adverse events (SAEs) will be tabulated by treatment group.

Laboratory values will be summarized by treatment group over time and overall.

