6.5.4 Additional Safety Variables

6.5.4.1 ECOG Performance Status

The ECOG Performance Status will be assessed according to the following categories:

Score	Characteristics
0	Asymptomatic and fully active
1	Symptomatic; fully ambulatory; restricted in physically strenuous activity
2	Symptomatic; ambulatory; capable of self-care; more than 50% of

	waking hours are spent out of bed
3	Symptomatic; limited self-care; more than 50% of waking hours are spent in bed
4	Completely disabled; no self-care; bedridden

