8.3 Analysis Populations

8.3.1 *Modified Intent-to-Treat (mITT) Population*

All randomized patients who met the study eligibility criteria at randomization will form the modified Intent-to-Treat (mITT) Population and will be analyzed according to the treatment group to which they were randomized. This population will be used to analyze all efficacy endpoints.

8.3.2 *Safety Analysis (SA) Population*

All randomized patients who received study treatments at least once, prior to progression (i.e. prior to date of progression) as assessed by investigator according to RECIST 1.1, will form the Safety Population and will be analyzed according to the treatment actually

received prior to progression. Note that patients who received only TheraSphere (no sorafenib) prior to progression do not receive full treatment of either protocol-defined treatment group, so will be analyzed as a separate group in the safety population. This population will be used in all safety reporting and analysis.

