8.7 Analysis of Safety

All safety analyses will be performed on the Safety Population.

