8.7.3 Clinical Laboratory Evaluations

Clinical laboratory results will be converted to SI units (except albumin will use the unit of g/dL and bilirubin will use the unit of mg/dL). Change from baseline to each visit assessed and end of study will be defined using the windowing method specified in Section 6.2.2, as the visit value minus the baseline visit. Laboratory test values at each assessment and for change from baseline to each assessment will be displayed using summary statistics (number of patients, mean, median, and standard deviation). Hematology, chemistry, and coagulation results will each be summarized separately.

All clinical laboratory data will be presented in listings. Within each listing, laboratory values outside the normal ranges will be flagged as either high or low. In addition, shift tables will be presented to display the shift in the normal range categories (low, normal, high) from baseline to the final evaluation. Baseline is defined as the latest non-missing value prior to randomization.

A shift table of baseline to each assessment by CTC grade (NCI CTCAE v4.0), and a table of laboratory parameters of CTCAE Grade 3 or higher that worsened from baseline will be summarized.

A shift table comparing the baseline ALBI score to the ALBI score at each time-point will also be summarized by treatment group.

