8.8 Additional Safety Analyses

A shift table comparing the baseline ECOG score to the ECOG score at each time-point will be summarized for the mITT population. This will be used to ascertain the number of patients with an ECOG score that worsens after baseline and any difference between the treatment groups.

Child-Pugh scores will be summarized for the mITT population in the same way as ECOG scores.

[REDACTED]

[REDACTED]

[REDACTED]

[REDACTED]

[REDACTED]

[REDACTED]

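### SAP 8.8 puts the ECOG and Child-Pugh shift tables on the mITT population, although the SAP and protocol assign safety analyses to the Safety Population

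*SAP*

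**What the plan says.** The general rule appears three times. SAP 8.3.2, after defining the Safety Population: "This population will be used in all safety reporting and analysis". SAP 8.7: "All safety analyses will be performed on the Safety Population". Protocol 10.2.4: "The safety analyses will be performed on the SA population".

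ECOG performance status, Child-Pugh and ALBI are all listed in the SAP under "6.5.4 Additional Safety Variables".

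SAP 8.8 then departs from the rule for two of the three. For ECOG: "A shift table comparing the baseline ECOG score to the ECOG score at each time-point will be summarized for the mITT population". For Child-Pugh: "Child-Pugh scores will be summarized for the mITT population in the same way as ECOG scores". The third stays inside 8.7, in section 8.7.3, with no other population named: "A shift table comparing the baseline ALBI score to the ALBI score at each time-point will also be summarized by treatment group".

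SAP 8.3.1 defines the set used in 8.8: "All randomized patients who met the study eligibility criteria at randomization will form the modified Intent-to-Treat (mITT) Population". These patients are analyzed by randomized group, and the population is introduced there for efficacy endpoints.

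**The concern.** The two populations differ in who is counted and how patients are grouped. mITT requires eligibility but not treatment. The Safety Population requires treatment before progression but not eligibility.

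A patient who was randomized in error, treated, and then deteriorated is therefore missing from the Child-Pugh and ECOG tables. Several eligibility criteria concern the liver: Child-Pugh of 7 or less, bilirubin of 2.5 mg/dL or less, no clinically evident ascites, not at risk of hepatic failure. A treated patient who failed one of these would be among those missing. Eligible patients who never received study treatment stay in the denominator, although they cannot show a treatment effect on liver function.

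Protocol 5.3, in its account of a published TheraSphere series, describes hepatic decompensation as a known risk of yttrium-90 microsphere therapy, so liver-function tables matter here. As planned, the Child-Pugh and ALBI tables would describe different sets of patients, and a reader comparing them would not be told why.

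**Working it through.** **Step 1. The populations side by side.**

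| | mITT (SAP 8.3.1) | Safety Population (SAP 8.3.2) |
|---|---|---|
| Eligibility at randomization | required | not required |
| Study treatment | not required | at least one, before investigator-assessed progression |
| Grouping | as randomized | as treated before progression; TheraSphere-only patients form a separate group |
| Tables | ECOG and Child-Pugh shifts (8.8) | adverse events (8.7.2), laboratory and CTCAE shifts and ALBI (8.7.3) |

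Moving the two tables to the Safety Population would bring in ineligible patients treated before progression, take out eligible patients not treated before progression, and regroup patients by treatment received.

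**Step 2. Is the exception declared?** SAP 8.8 gives no reason for it. The visible text of SAP 5.2, which lists changes to planned analyses, does not mention it. Subsection 5.2.4 is not visible, so a declaration there cannot be ruled out. Elsewhere the SAP names additional populations openly: section 8.7.1 puts exposure on mITT, PP and Safety together.

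**Step 3. Size of the omitted group.** The only sizing input is the sample-size assumption in protocol 10.1 and SAP 4.4: 520 randomized, 5% lost to follow-up, 5% randomized in error.

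- Plan's own figure: 520 × (1 − 0.05 − 0.05) = 468, which matches the effective sample size in SAP Appendix 5.
- Expected ineligible: 520 × 0.05 = 26. With 1:1 allocation, 26 / 2 = 13 per arm.
- Expected mITT: 520 − 26 = 494.

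The 26 is an upper limit on treated patients omitted at the planned rate, because some ineligible patients may not have been treated. If the true ineligible share were 1% to 10% (assumed range), the limit would be 520 × 0.01 = 5.2 to 520 × 0.10 = 52 patients.

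**Step 4. How many for liver reasons?** Not given. At 5% ineligible, an assumed liver share of 10% to 100% gives 26 × 0.10 = 2.6 to 26 patients, or 0.5% to 5% of those randomized.

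**Step 5. Untreated patients kept in.** The documents give no count, so this part cannot be sized.

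**The case against.** The best defense is that mITT was chosen on purpose. SAP 8.8 says the ECOG table is meant to show worsening and any difference between the arms, and Child-Pugh follows the same format. ECOG above 1 defines TTSP, and ECOG above 1 and Child-Pugh beyond B7 are TTUP events. Both endpoints are analyzed on mITT. A randomized-arm view is useful, and 8.8 is a separate section from 8.7. This is a good reason to keep an mITT version. It does not remove the conflict, because 8.3.2 covers all safety reporting and 8.8 states no exception.

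A second defense is that liver safety is already reported on the Safety Population, through adverse events, laboratory grades and ALBI. That is correct and limits the harm. The cover is incomplete: ALBI uses only bilirubin and albumin, whereas Child-Pugh adds ascites, encephalopathy and prothrombin time. The treatment-emergent window also closes 30 days after the last study treatment started before progression, or at subsequent HCC therapy if earlier.

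A third is that protocol 9.2.15.1.7 requires eligibility to be reconfirmed before TheraSphere is given, with fresh laboratory tests and ECOG. This makes treatment of liver-ineligible patients in that arm less likely, and is one more reason to read 26 as a ceiling.

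A reader might go further and infer that the patients most prone to liver failure are left out of the Child-Pugh table, and that its worsening rate is therefore too low. The documents do not support this. Failing any of 45 criteria removes a patient, and many are not hepatic (other cancer, prior radiation, interacting drugs, QTc, timing of TACE). Failure reasons are not reported, and eligible Child-Pugh B7 patients remain in the table.

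Any rate depends on what is assumed. Take 260 patients per arm, all treated, 13 of them ineligible, with 12% worsening among eligible patients and 30% among the ineligible (both assumed). The full rate is (247 × 0.12 + 13 × 0.30) / 260 = 12.9%, against 12.0% shown. If only 4 of the 13 carry the higher risk, it is (29.64 + 1.2 + 1.08) / 260 = 12.3%; with equal risk it stays at 12.0%. Nor is any effect on the comparison between arms shown, since ineligible patients are expected in both.

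**Conclusion.** The inconsistency is real and minor. SAP 8.8 puts two listed safety variables on mITT against SAP 8.3.2, SAP 8.7 and protocol 10.2.4, with no stated reason. The tables omit treated patients later found ineligible and include eligible patients who were never treated.

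At the plan's assumed 5%, the omission is at most about 26 of 520, about 13 per arm. That ceiling assumes the 5% holds and every ineligible patient was treated. The share ineligible for liver reasons is unknown, so neither a direction nor a size of change in the worsening rate can be claimed. The ineligible patients who were treated before progression remain visible in the adverse event, laboratory and ALBI outputs. The primary analysis of overall survival is unaffected.

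**What to change.** In SAP 8.8, produce the ECOG and Child-Pugh shift tables on the Safety Population exactly as SAP 8.3.2 defines it, including its as-treated grouping and separate TheraSphere-only group. This is the same set that governs ALBI, so ALBI needs no change. Keep the mITT version, by randomized arm, as a labeled supplement for the between-arm view. No new population is needed; a set such as any treatment at any time, by randomized arm, would match neither existing definition.

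The cost is a wording change in SAP 8.8 and one extra set of tables from data already collected.

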8.9.2 Association between $^{99m}\text{Tc-MAA}$ and Y-90 absorbed doses

The relationship between the pre-treatment and post-treatment ADs will be assessed separately for each AD endpoint listed in Section 6.6, using Bland-Altman analysis. The Bland-Altman analysis will calculate the 95% limit of agreement and will be performed by plotting the difference in AD (pre-treatment minus post-treatment) against the post-treatment AD. The figure will also present the number of patients.

In addition, a linear regression of the pre-treatment and post-treatment ADs (for each AD endpoint listed in Section 6.6) will be performed and Pearson's correlation coefficient will be calculated and displayed, along with the number of patients, on scatter plots.

8.9.3 Determination of Dose Volume Histogram (DVH) for tumoral and normal liver tissue volumes

The DVH values for tumor and normal tissue volumes will be determined. Summary statistics will be provided for both ^{99m}Tc -MAA and Y-90 values.

Additionally, the pre and post DVH value of D70 for tumor volumes and V30 for normal tissue volumes will be assessed for the same efficacy and safety endpoints as described in Section 8.9.1 in the same manner using logistic and Cox regressions.

9 COMPUTER SOFTWARE

All analyses will be performed by Labcorp using Version 9.1.3 or later of SAS® software. All summary tables and data listings will be prepared utilizing SAS® software.

For continuous variables, descriptive statistics (number of patients, mean, standard deviation, median, minimum, and maximum) will be generated. For discrete/categorical variables, the number and proportion of patients will be generated. The standard operating procedures of Labcorp will be followed in the creation and quality control of all data displays and analyses.

11 APPENDICES

11.1 APPENDIX 1: VARIABLE DEFINITIONS

Age will be calculated as the date of birth subtracted from the randomization date, divided by 365.25 [Age= (Randomization Date-DOB)/365.25]. Only the integer part of the result will be taken.

Weight will be displayed in kilograms, height will be displayed in centimeters, and temperature will be displayed in Celsius. Weights, heights, or temperatures recorded in alternate units will be converted to the units being displayed using standard conversion formulas.

11.2 APPENDIX 2: STATISTICAL ANALYSIS AND PROGRAMMING DETAILS

The SAS procedure LIFETEST will be used in the Kaplan-Meier analyses. Patients who did not have an event will be censored.

The following code will be used:

```
proc lifetest data=all method=km alpha=0.05 outsurv=interval;  
    time aval*censr(1);  
    strata trtp;  
    id usbjid;  
run;
```

The SAS procedure PHREG will be used in the Cox regression analysis of time-to-event endpoints. Patients who did not have an event will be censored. The SAS method of discrete will be used to handle ties.

The SAS procedure MIXED will be used for mixed modeling. The following code will be used:

```
proc mixed method = reml;  
class BASE TRT VISIT SUBJID;  
model CH= BASE TRT VISIT TRT*VISIT /s ddfm=kr;  
repeated VISIT/type=UN subject=SUBJID;  
lsmeans TRT*VISIT /slice=VISIT diff alpha=0.05 cl;  
run;
```

where BASE is the baseline score, TRT is the assigned treatment, VISIT is the visit based on the window mapping, CH is the change from baseline.

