⁴ Additional TS treatments may be administered only after progression if lesions are amenable to treatment

⁵ According to package insert at Weeks 1-4 for Control group patients and after all initial TS administrations for Treatment group patients only

⁶ Sorafenib to be stopped 7 days before subsequent TS administration on disease progression and restarted 2 weeks after TS is administered

⁷ If treatment commences within 14 days of randomization the clinical laboratory assessments are not required to be repeated.

⁸ The follow-up visits should be scheduled from the day of randomization. A window of ± 14 days is permissible from the scheduled date.

⁹ Progression of disease resulting in termination of further treatment

¹⁰ If available, ⁹⁹mTc-MAA SPECT or SPECT-CT taken as part of the TS planning and post TS treatment imaging (Y-90 SPECT-CT or Y-90 PET-CT or Y-90 PET-MRI) taken as part of the TS administration quality control, will be collected retrospectively for exploratory analysis

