6.2.2 Windows

For the purpose of statistical analysis, time windows will need defining for presentations that summarize values by visit. The windows for the visits following baseline will be constructed in such a way that the upper limit of the interval falls half way between the two visits (the lower limit of the first post-baseline visit will be Day 2), as shown below. The assignment of data to visit windows will use the relative day defined in Section 6.2.1.1.

Table 3 Analysis Windows for Assessments Performed at Eight Week Intervals

Week	Scheduled Day	Visit Window for Analysis (Days)
Week 8	57	2 – 85
Week 16	113	86 – 141
Week 24	169	142 – 197
...		
End of Study		Latest assessment available*

*Last assessment should be assigned to a Week X based on the visit windows as well as to the end of study evaluation.

If a patient has more than 1 assessment occurring in the same visit window, the data from the assessment closest to the scheduled day will be used. If 2 assessments have the same distance from the scheduled day, the data of the assessment after the scheduled day will be used. Note that the visit windows will not be used for time-to-event endpoints and subject-level tumor response endpoints (i.e. objective response rate and disease control rate).

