8.6 Analysis of Efficacy Parameters

8.6.1 Analysis of Primary Efficacy Variable

The primary efficacy analysis is of OS. OS rates will be derived from the Kaplan-Meier estimates for each treatment group; 6, 12, 18 and 24 month OS rates will be presented, together with 95% confidence intervals (CIs). Quartiles will be presented and 95% CIs will also be calculated on the quartiles for each treatment group. A log-rank (two-sided) test, converted to a z-score, will be used to compare OS between the two treatment groups at an overall two-sided alpha level of 0.05. The two-sided alpha level of 0.05 will be adjusted over the 2 planned interim analyses and final analysis (as described in Sections 7.4 and 7.5). The HR and corresponding two-sided 95% CI for the treatment effect will be computed from a Cox proportional hazards model. Plots of the Kaplan-Meier curves will be provided for each treatment group. This analysis will be performed on the mITT population (primary analysis) and PP population (secondary analysis).

The assumption of proportional hazards used to compute the HR for OS will be assessed. Firstly, a plot of log[-log (estimated probability of event-free survival)] versus log(time) will be examined, with nonparallel curves for the 2 treatment groups indicating non-proportional hazards. Also, a time-dependent covariate Cox regression model (i.e. adding a treatment group by time interaction) will be fitted and if the time-dependent covariate has two-sided p-value <0.15 piecewise HRs over distinct time periods will be calculated.

For each patient that has not known to have died, OS will be censored at the time of last contact date known to be alive.

Note that any patient who is still on the study and has not withdrawn or died at the data cut-off (DCO) date for the final analysis will have an additional survival contact on the day of DCO or within 2 weeks of DCO date, with Patient Contact/Overall Survival log and/or Confirmation of Death eCRF page to be completed accordingly. If patients are confirmed to be alive or if the death date is after the DCO date these patients will be censored at the date of DCO.

All patients should be followed for OS, however, if a patient has not known to have died and not been followed for OS for any reason (i.e. no contact date known alive on Patient Contact/Overall Survival log eCRF page), censoring date will be defined as the latest among the following dates recorded on the eCRF:

- Adverse event start and end dates

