8.6.2.1 Time to Progression (TTP) according to RECIST v1.1 criteria by investigator determination

TTP rates will be derived from the Kaplan-Meier estimates for each treatment group; 3, 6, 9, and 12-month TTP rates will be presented, together with 95% CIs. Quartiles will be presented and 95% CIs will be calculated on the quartiles for each treatment group. A log-rank (two-sided) test will be used to compare TTP between the two treatment groups at a 0.05 significance level. The HR and corresponding 95% CI will be computed from a Cox proportional hazards model. Plots of the Kaplan-Meier curves will be provided for each treatment group. This analysis will be performed on both the mITT and PP populations.

$$\text{TTP (Months)} = (\text{Date of event/censor} - \text{Date of Randomization} + 1) / 30.4375.$$

The censoring is performed in the following order:

- 1) If a patient does not have a baseline tumor assessment, then the TTP time will be censored at the randomization date, regardless of whether or not radiological disease progression (i.e. PD) has been observed.
- 2) If a patient received a subsequent HCC therapy before PD or in the absence of PD, the TTP time will be censored at the last valid (i.e. evaluable) post baseline radiological tumor assessment on or before the start date of the subsequent HCC therapy. If the patient has no valid post-baseline radiological tumor assessments on or before the start date of the subsequent HCC therapy, the patient will be censored at the randomization date.
- 3) If a patient is known not to have PD and did not receive subsequent HCC therapy, the TTP time will be censored at the date of death* or last valid post baseline radiological tumor assessment date in the absence of death, or at the randomization date if the patient does not have any valid post-baseline radiological tumor assessments or death.
- 4) If a patient had PD immediately after two or more missed visits (Note: a response of NE at a visit is not considered as a missed visit), the patient will be censored at the time of the last valid post baseline radiological tumor assessment date that occurred before the missed visits. If the patient has no valid post-baseline radiological tumor assessments before the missed visits, the patient will be censored at the randomization date.

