 - For example, if a patient had a tumor assessment at Week 8, but did not have tumor assessments at Weeks 16 and 24, and then had PD at the Week 32 assessment (i.e. after 2 missed visits), then the TTP time would be censored at the date of the Week 8 assessment.
 - Given the scheduled visit scheme of tumor assessments (i.e. every 8 weeks), the definition of 2 missed visits will equate to 16 weeks since the previous tumor assessment, or since the randomization date if no previous post-baseline tumor assessment.

* Note: Censoring at the date of death, in the above censoring rules, is according to US Food and Drug Administration (FDA) guidance⁸. However, a sensitivity analysis of TTP, excluding censoring at the date of death (i.e. censoring at the last valid post baseline radiological tumor assessment date instead) with all other censoring rules described above still used, will also be performed.

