8.6.2.2 Time to Untreatable Progression (TTUP)

TTUP rates will be derived from the Kaplan-Meier estimates for each treatment group; 3, 6, 9, and 12 month TTUP rates will be presented, together with 95% CIs. Quartiles will

be presented and 95% CIs interval will be calculated on the quartiles for each treatment group. A log-rank (two-sided) test will be used to compare TTUP between the two treatment groups at a 0.05 significance level. The HR and corresponding 95% CI will be computed from a Cox proportional hazards model. Plots of the Kaplan-Meier curves will be provided for each treatment group. This analysis will be performed on both the mITT and PP populations.

TTUP (Months) = (Date of event/censor – Date of Randomization +1)/ 30.4375.

The censoring is performed in the following order:

- 1) If a patient does not have a baseline tumor assessment, then the TTUP time will be censored at the randomization date, regardless of whether or not untreatable PD has been observed.
- 2) If a patient received a subsequent HCC therapy before untreatable PD or in the absence of untreatable PD, the TTUP time will be censored at the last valid (i.e. evaluable) post baseline radiological tumor assessment on or before the start date of the subsequent HCC therapy. If the patient has no valid post-baseline radiological tumor assessments on or before the start date of the subsequent HCC therapy, the patient will be censored at the randomization date.
- 3) If a patient is known not to have untreatable PD and did not receive subsequent HCC therapy, the TTUP time will be censored at the date of death or last valid post baseline radiological tumor assessment date in the absence of death, or at the randomization date if the patient does not have any valid post-baseline radiological tumor assessments or death.
- 4) If a patient had untreatable PD immediately after two or more missed visits (Note: a response of NE for a visit is not considered as a missed visit), the patient will be censored at the time of the last valid post baseline radiological tumor assessment date that occurred before the missed visits. If the patient has no valid post-baseline radiological tumor assessments before the missed visits, the patient will be censored at the randomization date.

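### SAP Appendix 2 specifies a discrete logistic tie method for estimates that SAP 8.6 labels Cox hazard ratios; the numerical effect is negligible for OS and small for the visit-based endpoints

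*SAP*

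**What the plan says.** SAP Appendix 2 (11.2) sets the software for all Cox models: "The SAS procedure PHREG will be used in the Cox regression analysis of time-to-event endpoints". It then fixes the tie handling: "The SAS method of discrete will be used to handle ties". No endpoint is exempted, so the instruction also reaches the covariate models (SAP 7.2), the subgroup forest plots (8.6.4) and the poolability models (8.6.5).

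For the primary endpoint, SAP 8.6.1 says: "The HR and corresponding two-sided 95% CI for the treatment effect will be computed from a Cox proportional hazards model". Sections 8.6.2.1 to 8.6.2.3, 8.6.3.2 and 8.6.6 say the same for TTP, TTUP, TTSP, TTDQoL and PFS.

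Three other statements decide how much the tie method matters:

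- Times are computed from calendar dates, for example "TTUP (Months) = (Date of event/censor – Date of Randomization +1)/ 30.4375" (8.6.2.2).
- SAP 6.2.2 does not collapse event times to nominal weeks: "Note that the visit windows will not be used for time-to-event endpoints".
- Protocol 3.0 lets follow-up visits move around the 8-week grid: "A window of ± 14 days is permissible from the scheduled date".

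Hypothesis tests come from the log-rank test, not from the Cox model. For TTP: "A log-rank (two-sided) test will be used to compare TTP between the two treatment groups at a 0.05 significance level" (8.6.2.1).

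**The concern.** PHREG offers several ways to handle tied event times. (How they behave is general statistical knowledge; the documents do not describe it.) EFRON and EXACT keep the proportional hazards model and treat ties as rounding of continuous time. DISCRETE changes the model: time is taken as truly discrete, and the coefficient is a log odds ratio of the event within each tied time point. With no ties the likelihoods coincide. With ties, the discrete estimate lies further from 1 and its standard error is larger.

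Time here is continuous and recorded in days, so ties come from rounding and from a shared visit calendar. Follow-up visits are scheduled from randomization every 8 weeks, so all patients are on the same grid in study time and progression dates can coincide. What is at stake is the meaning and, to a lesser degree, the size of the reported HRs and their confidence intervals. SAP 8.6.1 also plans a check of the proportional hazards assumption behind the OS hazard ratio. A model with discrete ties does not make exactly that assumption.

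**Working it through.** **The plan's own figures.** The documents give no figure for the tie method. The related figure is 417 deaths for 80% power at HR 0.754 (SAP 4.4). Simulating looks at 188, 250 and 417 deaths with Z boundaries 2.430, 2.429 and 2.093 (SAP Appendix 5) gives 79.9% power and a one-sided type I error of 0.0250. The figure reproduces, and it uses only the log-rank statistic.

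**Inputs from the documents.** 8-week (56-day) visits with a ±14-day window; 468 effective patients (SAP Appendix 5), 1:1; HR 0.754; control median OS 10.7 months; control median TTP 5.5 months (sorafenib arm of the placebo-controlled trial in Protocol 5.3).

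**Assumed.** Exponential times, uniform censoring at 3 to 40 months, a shorter control median of 3 months as a stress case, and the scatter of visit dates.

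**Step 1, closed form for the extreme case.** Suppose every event falls exactly on a scheduled visit day and the control median is 5.5 months.

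- Control event probability per visit: p0 = 1 − 2^(−56/(5.5 × 30.4375)) = 0.2069.
- Treated: p1 = 1 − (1 − 0.2069)^0.754 = 0.1604.
- Odds ratio = (0.1604/0.8396)/(0.2069/0.7931) = 0.732, against a hazard ratio of 0.754.
- On the log scale: ln 0.732 / ln 0.754 = 1.10, an inflation of about 10%.

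The odds ratio is 0.724 at a 4-month median (about 15%) and 0.713 at 3 months (about 20%).

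**Step 2, the same events spread over the permitted window.** If each visit's events fall evenly on 29 days (±14), the control probability per day is about 0.0080 and the odds ratio is 0.7533, almost equal to the hazard ratio.

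**Step 3, paired simulation.** The same simulated data sets (80 per case, true HR 0.754) were fitted with the discrete and Efron likelihoods. The last column is ln(ratio)/ln(Efron HR).

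| Endpoint, control median | Visit dates | Discrete | Efron | Ratio | Inflation of log HR |
|---|---|---|---|---|---|
| OS, 10.7 months | daily death dates | 0.7463 | 0.7466 | 0.9997 | 0.1% |
| TTP, 5.5 months | uniform ±14 days | 0.7348 | 0.7356 | 0.9989 | 0.4% |
| TTP, 5.5 months | SD 3 days | 0.7558 | 0.7579 | 0.9972 | 1.0% |
| TTP, 5.5 months | all exactly on schedule | 0.7218 | 0.7452 | 0.9686 | 11% |
| TTP, 3 months (assumed) | uniform ±14 days | 0.7530 | 0.7543 | 0.9982 | 0.6% |
| TTP, 3 months (assumed) | SD 3 days | 0.7588 | 0.7626 | 0.9950 | 1.8% |
| TTP, 3 months (assumed) | all exactly on schedule | 0.7097 | 0.7543 | 0.9408 | 22% |

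Within a row the difference comes from the same data, so it is precise even though both estimates vary around 0.754. With spread dates, about 70 to 90% of events share a day with another event, but the tied sets are small (the largest is about 7 to 23 events), which is why the shift is small.

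**Step 4, clustering between these extremes.** Log HR inflation was 0.5 to 0.7% with a visit SD of 5 to 7 days, about 1.7% with SD 2 days and 3.3% with SD 1 day. It was 5 to 7% if patients always return on the same weekday.

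**Step 5, tests and intervals.** In an exact-schedule run where the log HR rose 13%, its standard error also rose 13%. Their ratio hardly moves, so whether the 95% interval excludes 1 hardly changes.

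**The case against.** The strongest defence is that nothing decided in this trial depends on the option. Time-to-event endpoints are compared by log-rank, and the score test of the discrete model is itself the log-rank test with hypergeometric variance, so pairing the two is coherent. That stands, and it limits the point to estimation and labelling. It does not make an odds ratio a Cox hazard ratio.

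The second defence concerns size. A reader might infer that the HRs for TTP, TTUP, TTSP, TTDQoL and PFS will be visibly exaggerated. The documents do not support this. A visible shift needs event times collapsed onto nominal visit days; SAP 6.2.2 excludes that for time-to-event endpoints, and Protocol 3.0 allows ±14 days. No document gives a visit SD, and exact-day attendance across up to 105 centers is not plausible. Several of these endpoints also include events that need not fall on a visit: deaths in PFS and TTDQoL, and sorafenib intolerance, contraindications or death due to progression in TTUP. These dilute the ties further. All of this stands.

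It would also be too strong to say that a different model is fitted for every HR in the trial in any meaningful sense. Where event times are untied the two likelihoods are identical, and for OS the difference is negligible.

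**Conclusion.** The point holds as a mismatch between SAP Appendix 2 and SAP 8.6. The specified option fits a discrete logistic model at ties, the estimate is called a Cox hazard ratio, and discrete time does not describe data recorded in days. The shift was away from 1 in every case run, so it is a one-directional bias, but a small one:

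- **OS:** about 0.03% on the HR scale.
- **Visit-based endpoints, dates spread over ±14 days:** under about 1% of the log HR, a change in the third decimal of the HR.
- **Visits clustered on the same day or weekday:** a few percent, up to about 7%.
- **Every visit exactly on schedule:** mostly 11 to 16%, somewhat less for stronger effects at a 5.5-month control median, and about 20% if that median were as short as 3 months. This is a bounding case, not an expectation.

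These sizes rest on the assumed visit scatter, exponential times and censoring. A reader might infer that significance or the primary conclusion is at risk. It is not: log-rank p-values, the efficacy boundaries, the 417-death power calculation and the testing hierarchy do not use the Cox estimate. This is a minor correction.

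**What to change.** In SAP Appendix 2, replace the discrete tie method by TIES=EFRON (or TIES=EXACT) for every estimate labelled HR, including the covariate, subgroup and poolability models. Appendix 2 then matches SAP 8.6 and the planned proportional hazards check.

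The cost is one option in the programs and a documented change. Documentation matters because SAP version 6.0 is dated 15 September 2022, after the 30 April 2022 limit for the final analysis, and the documents do not say whether Cox outputs already existed. If discrete outputs exist, keep them only as a check beside the Efron results. If the discrete method is retained, label its result as an odds ratio of discrete hazards that approximates the HR. No test, boundary or sample size needs to change.
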